Corneal cross-linking is performed with either the corneal epithelium intact or de-epithelialized in patients with progressive keratoconus. The ophthalmic solution *RitSight*™ is applied onto the cornea and its concentration into the cornea monitored by C4V CHROMO4VIS™ system with theranostic software module (v. 2.0). After the pre-set time for application of riboflavin onto the cornea is ended (i.e., 15 min. for epi-off CXL and 20 min. for epi-on CXL protocol), the cornea is illuminated by the C4V CHROMO4VIS™ system using 5.4 J/cm² UV-A energy dose (10 mW/cm² for 9 minutes).

Primary End Point and Outcome Measure

Time point 12 months: validation of the theranostic imaging biomarkers.

Validation of the combined use of the theranostic imaging biomarkers. True positives, false positives, true negatives and false negatives were evaluated in order to determine the ability of the theranostic imaging biomarkers, including both the *riboflavin score* and *theranostic score*, to predict the propensity of CXL treatment in flattening the K_{\max} value (D) by more than 0.1 D at 12 months postoperatively. True positives, false positives, true negatives and false negatives will be evaluated.

Secondary Outcome Measures

- Efficacy: Change of Maximum Keratometry (K_{\max}) assessed by corneal topography at 12-months.
- Safety: change of Endothelial Cell Density (ECD) assessed by specular microscopy at 12-months.

Exploratory Outcome Measures

- Change of Uncorrected Distance Visual Acuity (UDVA) assessed by ETDRS at 12-months.
- Change of Corrected Distance Visual Acuity (CDVA) assessed by ETDRS at 12-months.
- Change of Manifest Refraction assessed by ETDRS at 12-months.
- Change of primary and secondary outcome measures in either stratification group at 12-months.

Adverse events

Any adverse event (AE) occurring in a participant enrolled into the clinical trial shall be reported in detail on the CRF according to the ICH Guidelines and the MDCG 2020-10-2 Guidance safety report form. The Medical Dictionary for Regulatory Activities (MedDRA®) is used to code all AEs.

Study Records/Source Documents/Personal Data protection

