Numerical variables will be summarized as mean and standard deviation (SD) and as median and interquartile range (IQR). Categorical variables will be represented as frequencies and proportions. For numerical variables, paired Student t-test or Wilcoxon signed-rank test will be used to compare the distributions preoperatively and 12-months postoperatively. Bonferroni correction will be

applied to analysis of exploratory outcome measures of stratification groups. For all reported AEs, the data shall be presented with events listed in order of decreasing frequency.

Sites of Investigation

- Azienda Ospedaliera Universitaria Careggi, Università di Firenze
- Azienda Ospedaliera Universitaria Policlinico G. Martino, Università di Messina
- Azienda Ospedaliera Universitaria Mater Domini, Università Magna Graecia di Catanzaro

Coordinator Site of Investigation

- Azienda Ospedaliera Universitaria Mater Domini, Università Magna Graecia di Catanzaro

List of principal investigators

[name], ophthalmologist (UniFI)

[name], ophthalmologist (UniME)

[name], ophthalmologist (UniCZ)

Declaration of the Sponsor on the sources and types of financial, material and other support

The Sponsor has provided the clinical investigators and Site of Investigations with the Protocol (including Case Report Forms), the investigator's brochure, confidentiality, personal data safety and sponsor agreements, and any other documentation, which is necessary to complete the Study.

[figure not shown]
The Sponsor has verified in local audit that each clinical center has a designated clinical area and equipment as well as that the investigators are qualified and experienced to perform the present Study.

The Sponsor loans, free-of-charge, the medical devices and the equipment required to perform treatment to the Investigators/Institutions for the entire duration of the trial. The free of charge supply of these materials does not influence the scientific, technical and procedural autonomy of the Investigators and Study staff. The medical devices used in this Study will be stored and handled according to the applicable Laws. The equipment will be handled with care and used exclusively in the clinical trial. The Sponsor will train the investigators on how to use these devices. The Sponsor undertakes the liability insurance required for each subject enrolled in the Study.

Regulatory aspects and Funding Sources

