By revising the clinical data on the efficacy of the gold standard protocol, i.e., the *Dresden protocol*, the K_{\max} decreases by -1.0 D and -1.7 D in almost 50% of cases at 1-year postoperatively; the corrected visual acuity (CDVA) on average stabilizes (mean change of -0.05 LogMAR in 50% of cases) and the manifest refraction on average changes by +0.50 D (in general, the reduction of the myopic sphere equivalent is between +0.2 D and +0.7 D) in the same period. The central corneal thickness on average remains almost unchanged (+4 µm) compared to the preoperative period at 1 year after treatment. However, epithelial removal is the predisposing factor to the most frequent and major complications of the standard protocol, such as infectious keratitis, sterile corneal infiltrates, corneal scarring, which may cause vision loss.⁵ An additional risk factor in the standard protocol is the treatment of corneas with a central corneal thickness lower than 390 µm, due to the risk of inducing phototoxic damage to endothelial structures.

In the last decade, an increasing number of treatment protocols have been developed in order to avoid epithelial removal and to reduce treatment time. Currently, CXL can be performed according to various treatment protocols, which are classified into two main groups, i.e., the protocols that require corneal de-epithelialization (also called EpiOFF) and those that do not require epithelial removal (also called EpiON or transepithelial protocols). Each type of surgical protocol, both EpiOFF and EpiON, in turn may vary according to the method and time of riboflavin application and the method and time of UV-A irradiation of the cornea.

Currently, CXL is well established to treat progressive keratoconus and tens of thousands of treatments are performed yearly worldwide. Half of patients claim to have their quality of life much more improved after corneal cross-linking treatment and the procedure has proven to be a valid

⁵ Alio JL et al. Corneal cross-linking and infectious keratitis: a systematic review with a meta-analysis of reported cases. J Ophthalmic Inflamm Infect 2013;3(1):47.

therapy in halting keratoconus progression and drastically reducing the need of keratoplasty for thousands patients worldwide.

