In this study, patients with progressive keratoconus receives a single dose of the ophthalmic solution RitSight™ (CE0477) delivered into the cornea manually for at least 15 minutes and treated by using the C4V CHROMO4VIS™ system with the theranostic software module while they are observed and tested for a period of 12 months after treatment to assess correlation between the theranostic imaging biomarker and the K_{max} flattening.

Follow-up for each participant is twelve months after treatment. The interval is long enough to observe treatment efficacy as well as any effect or complication induced by the innovative corneal cross-linking procedure performed by using the theranostic UV-A medical device in a participant.

Study Participants

The inclusion criteria are: diagnosis of progressive keratoconus. Participants with 18-40 years old are eligible, all genders.

According to the most recent scientific literature⁹, the criterion to determine progression of keratoconus is based on providing at least one of the following types of evidence:

- at least two Placido disk corneal topography measurements showing at least +1.00 D steepening of the K_{max} value in the last year or longer interval period.
- at least two central corneal thickness (CCT) measurements showing at least -10 µm change in in the last year or longer interval period.

⁹ Ferdi A, et al. Keratoconus Natural Progression: A Systematic Review and Meta-analysis of 11 529 Eyes. Ophthalmology 2019;126:935-945

The exclusion criteria are: corneal apex steeper than 63 D, corneal thickness thinner than 400 µm; corneal scarring; descemetocèle; history of herpetic keratitis; concomitant eye diseases; inflammatory eye diseases; glaucoma; cataract; nistagmus; pregnancy; breast feeding.

The study does not accept healthy volunteers.

If both eyes of a participant are eligible, the eye with lower CDVA will be chosen as the study eye.

Study Arm

One study arm receiving either corneal cross-linking treatment after epithelial debridement (“Theranostic Epi-OFF CXL”) or transepithelial corneal cross-linking treatment (“Theranostic Epi-ON CXL”). Only one eye of each participant is designated as the study eye.

Discontinuation of contact lens wear

Participants must discontinue the use of contact lenses from seven days before baseline visit to 3 months follow-up; thereafter, they must discontinue the use of contact lenses at least seven days before the remaining follow-up visits at day-180 and day-360.

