Outcome Measures and Assessments

Both eyes of each participant will be evaluated at baseline (i.e., before treatment) to assess eligibility; only one eye for each participant will be treated by corneal cross-linking (“study eye”). The study eye of each recruited subject will be assessed to investigate the primary and secondary outcome measures.

Assessment of the novel theranostic-guided riboflavin/UV-A corneal cross-linking treatment modality will be determined objectively by a comprehensive eye examination, measurement of corneal topography and corneal endothelial microscopy.

Follow-up assessments will be performed on day 7, 30, 90, 180 and 360 after treatment.

At baseline (assessment of both eyes) and all the subsequent follow-up visits (assessment of “study eye” only) each subject recruited in the study will undergo the following examinations:

- 1) Uncorrected Distance Visual Acuity (UDVA) tested using the ETDRS chart.
- 2) Corrected Distance Visual Acuity (CDVA) tested using the ETDRS chart.
- 3) Manifest Spherical Equivalent Refraction (MSER) tested with ETDRS chart.
- 4) Measurement of corneal curvature (K_{\max} , K_{steep} , K_{flat}) and corneal thickness (CCT) using a combined Placido-disk computerized corneal topography.
- 5) Measurement of endothelial cell density (ECD) using the corneal specular microscopy.
- 6) Slit lamp bio-microscopy of the ocular surface and the anterior segment of the eye.

At baseline (assessment of both eyes) and at last follow-up visit (12-months), each subject recruited in the study will undergo also ocular tonometry and indirect ophthalmoscopy.

The study visits and the battery of tests to be performed at each visit are fully described in next section.

The investigators may opt to perform additional, no-contact, instrumental testing, as a part of their standard of care practice in patients with keratoconus, which are not due for protocol. A rationale for performing additional instrumental testing in participants shall be added in the corresponding box of the CRF (Annex 1).

Study Visits

Each participant will undergo treatment and six study visits. A tabulated summary of the study visits for study groups including the assessments to be performed at each visit is summarized below:

Time	baseline	day 0	day 7	day 30	day 90	day 180	day 360
Description	Visit 1	Treatment	Visit 2	Visit 3	Visit 4	Visit 5	Visit 6
Informed consent	X						
Medical history	X						
UDVA	X	X	X	X	X	X	X
CDVA	X	X	X	X	X	X	X

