If the bandage contact lens that is placed on the patient's eye on the day of treatment falls out or becomes dislodged, the patient shall be advised not to replace it and to contact the Principal Investigator of the Site of Investigation immediately.

Study Product Packaging and Storage

The Site of Investigation will receive an UV-A medical device and enough bottles of the RitSight ophthalmic solution to treat all the planned participants. Each Site will receive at least 20 bottles of RitSight™. The carton box of each bottle will be labelled with a white printed label bearing the following information in English:

- **For Clinical Trial Use Only**
- **Study code:** RSKC001
- **Acronym:** ARGO
- **Sponsor:** RegenSight srl

RegenSight

For Clinical Trial Use Only

Study code: RSKC001

Acronym: ARGO

Sponsor: RegenSight srl

The participant box shall be stored in a locked cabinet/locked room at the Site of Investigation's operating room between 4°C to 25°C. Only the principal investigator of the Site will have access to these products during the course of the study. He/She will annotate the stratification number for that participant in the respective CRF.

Test Article Accountability

The principal investigator of the Sites of Investigation will maintain accurate records of receipt of all study products, including dates of receipt. In addition, accurate records will be kept regarding when the study product (participant kit) is dispensed and used by each patient in the study. Reasons for departure from the expected dispensing regimen or dispensing of an extra kit must also be recorded. At the completion of the study, to satisfy regulatory requirements regarding accountability, all study products records will be reconciled.

Study assessments

Demographic Data/Medical History

Key-coded personal details, gender, age, details of general health and eye health and current medication.

Efficacy Assessments

Efficacy data will be identified by using objective and subjective methodologies, as described in the following:

- Measurement of **corneal curvature** with Placido disk topographer will assess changes of the K_{max} after treatment.

Safety Assessments

Safety data will be identified by using objective methodologies, as described in the following:

- Measurement of **Corrected Distance Visual Acuity** (CDVA) with ETDRS chart at a test distance of 4 m will assess changes of the CDVA after treatment.

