Corneal specular microscopy: endothelial cell density (ECD, cell/mm²) count will be done by using corneal specular microscopy. The investigator will record the ECD at each visit and will fill the corresponding CRF. This test is performed to provide evidence of corneal cells integrity after treatment.

Other outcome measures

Efficacy [Time Frame: 12-months]

- Change of Manifest Refraction assessed by ETDRS at 12-months.

Manifest Refraction: manifest refraction will be determined using a standard ETDRS chart under photopic conditions (with the luminance of the test at 85 cd/m²) at a test distance of 4 m. The Manifest Refraction will be assessed by using trial lenses and will be expressed in diopters (D). This test is performed to provide evidence of optical focusing properties change after treatment.

- Change of Best-Spectacle Corrected Visual Acuity (CDVA) at 12-months.

Corrected Distance Visual Acuity (CDVA): CDVA will be determined using a standard "Early Treatment Diabetic Retinopathy Study" (ETDRS) chart under photopic conditions (with the luminance of the test at 85 cd/m²) at a test distance of 4 m. The CDVA will be expressed in LogMAR. The ETDRS test incorporates specific design criteria to make it more accurate than the Snellen or Sloan acuity tests. These include:

- Same number of letters per row (five letters per row);

- Equal spacing of the rows on a log scale (the rows are separated by 0.1. log unit);
- Equal spacing of the letters on a log scale;
- Individual rows balanced for letter difficulty.

The patient starts at the top of the chart and begins to read down the chart. The patient reads down the chart until he or she reaches a row where a minimum of three letters on a line cannot be read. The patient is scored by how many letters could be correctly identified and by the LogMAR of the line with ≥ 3 letters he/she is able to read.

- Change of Unorrected Visual Acuity (CDVA) at 12-months.

Uncorrected Distance Visual Acuity (UDVA): UDVA will be determined using a standard “Early Treatment Diabetic Retinopathy Study” (ETDRS) chart under photopic conditions (with the luminance of the test at 85 cd/m²) at a test distance of 4 m. The UDVA will be expressed in LogMAR. The ETDRS test incorporates specific design criteria to make it more accurate than the Snellen or Sloan acuity tests. These include:

- Same number of letters per row (five letters per row);
- Equal spacing of the rows on a log scale (the rows are separated by 0.1. log unit);

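### Choosing the worse-seeing of two eligible eyes builds a small spurious gain into 12-month CDVA change if Visit 1 is the reference, and the plan does not name the reference

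*Combined protocol and SAP*

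**What the plan says.** Study Participants sets the rule for choosing the eye: "If both eyes of a participant are eligible, the eye with lower CDVA will be chosen as the study eye". Outcome Measures and Assessments says when the two eyes are compared: "Both eyes of each participant will be evaluated at baseline (i.e., before treatment) to assess eligibility". From then on only the study eye is assessed. The visit table and the Visit 1 section give this visit the label Baseline.

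CDVA has two roles. The Synopsis lists it among the exploratory outcomes: "Change of Corrected Distance Visual Acuity (CDVA) assessed by ETDRS at 12-months". Safety Assessments also includes it, as a measurement that "will assess changes of the CDVA after treatment". On the scale, Other outcome measures says: "The CDVA will be expressed in LogMAR".

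For numerical variables, the Data Analysis part of the Synopsis says that a "paired Student t-test or Wilcoxon signed-rank test will be used to compare the distributions preoperatively and 12-months postoperatively". There is one study arm, split between two cross-linking protocols, with no untreated group.

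The visit table also marks UDVA and CDVA in the day-0 treatment column. Neither the Treatment (day 0) text nor the step list in the Treatment section mentions an acuity test, so the time of that reading relative to treatment is not stated. No section says which pre-treatment reading is the reference for change.

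**The concern.** An eye picked because its reading was the worse of two is, on average, an eye whose reading erred in the adverse direction that day. Measured again, the same eye is expected to read better even if nothing has changed. If the reading that selected the eye is also the reference for change, this regression to the mean enters the 12-month CDVA result as improvement.

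A paired test cannot separate it from a treatment effect. Nothing in the design can be used to subtract it either: there is no untreated group, and the fellow eye is not followed. The average gain would be overstated and a little true loss could be hidden, in the one acuity measure that the plan lists for safety. UDVA is taken at the same visit and shares part of the effect, to the extent that its error goes with the CDVA error.

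**Working it through.** The plan has no figure of its own to reproduce here. It gives no CDVA reading error, no between-eye SD and no share of participants with two eligible eyes. Its only power statement concerns the AUC.

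**Inputs from the documents**
- Yardstick: the background section on cross-linking cites, for the standard protocol at one year, a "mean change of -0.05 LogMAR in 50% of cases".
- Letter size: five letters per row and 0.1 log unit between rows (Other outcome measures), so one letter is 0.02 LogMAR.

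**Inputs assumed**
- Reading error per eye, se: 0.05-0.10 LogMAR.
- SD of true CDVA between the eyes of one person, sw: 0.10-0.20 LogMAR (the true difference between eyes then has SD sw√2).
- Share with two eligible eyes, f: 0.25-0.50.
- Errors are normal and independent between eyes, with one reading per eye.

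**Formula.** Let X = true value + error for each eye, and choose the eye with the higher LogMAR. The expected error in the chosen reading is

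Cov(e₁, X₁ − X₂) / SD(X₁ − X₂) × E|Z| = 0.798 × se² / √(2(sw² + se²)).

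This error is not expected to recur at 12 months, so it appears as a gain of that size.

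**Results in participants with two eligible eyes**

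| se | sw | calculation | spurious gain (LogMAR) |
|---|---|---|---|
| 0.05 | 0.20 | 0.798 × 0.0025 / √0.085 | 0.0068 |
| 0.07 | 0.15 | 0.798 × 0.0049 / √0.0548 | 0.0167 |
| 0.10 | 0.10 | 0.798 × 0.0100 / √0.04 | 0.0399 |

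**Cohort mean.** The low end is 0.25 × 0.0068 = 0.002 LogMAR and the high end is 0.50 × 0.0399 = 0.020 LogMAR. That is about 0.1 to 1 letter, or about 3% to 40% of the 0.05 LogMAR yardstick.

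**Simulation check.** Each trial had 42 participants, no true mean change and an assumed SD of 0.10 LogMAR for real within-eye change, with 4,000 trials per setting. One mid-range setting was se 0.08, SD of the true between-eye difference 0.20 (sw = 0.20/√2 = 0.14) and f 0.5.
- The formula gives 0.5 × 0.798 × 0.0064 / √0.0528 = 0.011 LogMAR. The simulation gave 0.011, which is 22% of the yardstick.
- A falsely significant gain occurred in 6.4% of trials, against a nominal 2.5%.
- Eyes showing a loss above 0.2 LogMAR were 8.0%, against 9.3% with an independent reference reading. In 42 participants that is 0.013 × 42 = 0.5 of an eye.

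Across all the settings simulated, counting change from a pre-treatment reading not used for selection gave a mean change of 0.000 LogMAR and a two-sided rejection rate of 4.4-5.4%.

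**The case against.** The strongest objection is that the plan never says change is counted from Visit 1. The analysis text speaks only of preoperative values, and a day-0 reading taken before treatment would also be preoperative. The plan does not say how many readings decide the choice, and averaging several would shrink the error. This stands: the documents show an unspecified reference, with Visit 1 the natural default because of its label. They do not show that the bias will occur.

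A reader might infer that the artefact must always look like improvement. That holds only in expectation, and only if lower CDVA means worse vision. CDVA is in LogMAR, where a lower number is better vision. Read literally on that scale, the rule picks the better eye and the artefact becomes a loss. Worse vision is the more natural reading, but the text does not settle it.

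A reader might also infer that naming day 0 as the reference is enough. It is not. The timing is unstated, and the text under the adverse-event table expects epithelial removal to reduce vision. A reference taken after removal could create its own spurious gain, possibly a larger one.

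It is also fair to say that the effect is small. The cohort shift is 1-10% of the 0.2 LogMAR that corresponds to the loss category of more than two lines in the literature adverse-event table. The 0.05 LogMAR yardstick comes from the literature and is not a trial target. CDVA change has no success threshold and no part in the sample size. ECD, slit lamp and adverse-event recording cover safety without being chosen on CDVA.

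**Conclusion.** The point holds as a conditional one of minor weight. If Visit 1 is the reference and lower CDVA means worse vision, participants with two eligible eyes carry an expected spurious CDVA gain of 0.007-0.040 LogMAR, and the cohort mean carries 0.002-0.020 LogMAR. Both ranges rest on assumed values for reading error, between-eye SD and the share with two eligible eyes. The effect is near the low end when the eyes truly differ a good deal or few participants qualify in both. The high end needs the largest error, the smallest between-eye SD and the highest share together.

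Only CDVA, as an exploratory outcome and a safety assessment, and partly UDVA are affected. The documents do not support extending the point to the primary biomarker analysis or to the Kmax and ECD changes, because the eye is not chosen on those readings. Nor do they support a claim that visual safety cannot be judged.

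**What to change.** Four additions to the text:

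1. In Study Participants, define lower CDVA as worse vision, that is, the higher LogMAR value.
2. State that the Visit 1 CDVA serves only to choose the study eye.
3. In the day-0 procedure, state that the CDVA and UDVA already marked in the visit table are taken before anaesthetic drops, epithelial removal and any other treatment step. In the analysis section, name them as the reference for 12-month change in every participant.
4. As a check, show CDVA change separately for participants with one and with two eligible eyes.

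No new test or visit is needed, because the day-0 acuity is already scheduled. The cost is an edit to the day-0 procedure as well as to the analysis text, and the sites must keep to the stated timing. If a pre-treatment day-0 reading is missing, use Visit 1 and flag that participant's change as subject to this bias.
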